1.1 Summary of Design

The Navigator study is a pragmatic randomized controlled trial (RCT) conducted at an urban academic teaching hospital (St. Michael's Hospital) and an urban community teaching hospital (St. Joseph's Health Centre) in Toronto, Canada. Recruitment began in October 2021 and total recruitment is estimated to be completed by December 2024.

Eligible patients must be 18 years of age or older, be admitted to any medical or surgical service (excluding psychiatry and obstetrics), and be identified as experiencing homelessness (as per the Canadian definition of homelessness) at the time of admission or anytime during the hospital admission. Patients will not be eligible if they are unable to provide informed consent or were connected with a Homeless Outreach Counsellor (HOC) prior to the initiation of the RCT and have received services from the HOC within 90 days preceding their current admission

Participants are randomized by a third-party randomization service (randomize.net). This service will assign participants to either the intervention or the usual care arm using permuted-block randomization, with a 1:1 allocation ratio and random permuted block sizes of 6 or 8. This process will maintain balanced group sizes between the intervention and usual care arms at intermediate points in the recruitment process and minimize the possibility of the research team predicting study allocation.

Participants randomized to the intervention arm are assigned to a HOC, who connects with participants as early as possible during the admission and provides support for 90 days after hospital discharge (or beyond 90 days for certain patients, if the HOC deems this to be necessary and/or appropriate). HOCs activities include (1) making connections and referrals to community-based providers, (2) supporting and advocating for patients during the hospital stay and discharge process, (3) supporting patients with health-related matters during the post-discharge period, (4) supporting patients with social-related matters during the post-discharge period, and (5) transferring patient-related information to other healthcare and community-based providers.

Participants in the usual care arm are discharged without support from a HOC. However, all participants still receive standard supports from Care Transition Facilitators (CTFs) and/or social workers. Although CTFs and social workers help patients during their hospital stay to arrange discharge plans and make follow-up arrangements, they do not typically work with patients after hospital discharge.

It is not possible to blind participants, HOCs, or healthcare teams given the active and collaborative nature of the intervention. However, data collectors and data analysts are blinded to the allocation of participants. The research team member who performs study allocation for a participant will not be involved in the 30-day follow-up interview for that participant.

1.2 Primary Research Question

Among adults experiencing homelessness admitted to any medical or surgical service (excluding psychiatry and obstetrics), does the Navigator Program increase follow-up visit rates with a primary care provider [PCP] (physician or nurse practitioner) within 14 days of hospital discharge, as compared with usual care?

1.3 Secondary Research Questions

Among adults experiencing homelessness admitted to any medical or surgical service (excluding psychiatry and obstetrics), what are the effects of the Navigator Program on the number of emergency department visits and the composite of hospital re-admission or all-cause mortality following hospital discharge, as compared with usual care?

1.4 Exploratory Research Questions

Among adults experiencing homelessness admitted to any medical or surgical service (excluding psychiatry and obstetrics), what are the effects of the Navigator Program on their care transition experience, number of days in hospital post-discharge, time to re-admission or death, difficulties meeting subsistence needs, visit rates to non-PCP providers, medication adherence, rates of connection to community-based case managers, rates of leaving against medical advice, and overall health status and quality of life following hospital discharge, as compared with usual care?

2 Outcomes

2.1 Primary Outcome

The primary outcome is follow-up with a PCP (physician or nurse practitioner) within 14 days of hospital discharge. This outcome was chosen given the unique and substantial barriers to primary care access faced by the homeless population and the fact that timely access to primary care after hospitalization is associated with better outcomes. In-person visits, virtual encounters, and phone calls will all be considered. The primary outcome will be ascertained using three data sources: a) through participant self-report at the 30-day interview; b) phone calls to PCP offices, and c) verification in the OHIP and Community Health Center Databases at ICES. PCP follow-up documented in any of the three data sources will be considered sufficient to meet the primary outcome criterion. Definitions, self-reported measures, and scoring algorithms of the primary outcome and all other outcomes are described in Appendices 1 and 2.

2.2 Secondary Outcomes

The secondary outcomes are listed below, collected using administrative databases at ICES. For participants who cannot be linked to databases at ICES, administrative data will be obtained from St. Michael's Hospital and St. Joseph's Health Centre.

- 1. Number of emergency department visits within 30 days post-discharge
- 2. Number of emergency department visits within 90 days post-discharge
- 3. Composite measure of any re-admission or all cause-mortality within 30 days post-discharge
- 4. Composite measure of any re-admission or all cause-mortality within 90 days post-discharge

2.3 Exploratory Outcomes

Exploratory outcomes will be collected using hospital discharge summaries, participant self-report at the 30-day interview, and ICES or other administrative databases

2.3.1 Hospital Discharge Summaries

1. Participant leaving against medical advice (during the initial hospitalization during which they are randomized)

2.3.2 Participant's Self-Report at 30-Day Interview

- 1. Self-reported quality of care transition (3-item Care Transitions Measure, CTM-3) after hospital discharge at the time of the 30-day interview
- 2. Self-reported change in difficulties meeting subsistence needs (Competing Priorities measure from RAND Course of Homelessness Study) at the time of the 30-day interview relative to baseline
- 3. For participants who did not previously report contact with a case manager in the 30 days prior to the baseline interview, connection to a case manager in the community at the time of the 30-day interview
- 4. Medication adherence (eight-item Morisky Medication Adherence Scale, MMAS-8) at the time of the 30-day interview
- 5. Change in health status (EQ-5D-3L; European Quality of Life Five Dimension Three Levels) at the time of the 30-day interview relative to baseline
- 6. Change in quality of life (EQ-5DVisual Analogue Scale) at the time of the 30-day interview relative to baseline

2.3.3 ICES or Other Administrative Databases

- 1. Total number of days spent in hospital(s) after index admission within 90 days post-discharge
- 2. Total number of days spent in hospital(s) after index admission within 180 days post-discharge
- 3. Time in days to all-cause re-admission or mortality after discharge (up to 180 days post-discharge)
- 4. Attendance of any non-PCP healthcare appointment made at the time of discharge (up to 180 days post-discharge)

3 Analysis Sets

3.1 Intention-to-treat sample

All analyses will follow the intention-to-treat principle. All randomized participants who are discharged alive contribute outcome data to the analysis based on their randomized group, regardless of compliance.

The primary outcome can only occur in patients who are discharged alive. Thus, participants will be excluded from the analysis if:

- (a) they die during the initial hospitalization during which they are randomized, or
- (b) they are never discharged from hospital and remain hospitalized 30 days after the final study participant is randomized

4 Statistical Methods

4.1 Sample Size Justification

We assumed that the 14-day PCP follow-up rates after hospital discharge among people experiencing homelessness receiving usual care would be approximately 2/3 that of low-SES patients in a study conducted at two urban academic hospitals (=2/3 of 48%=32%). Sample sizes of 256 participants per study arm achieve 80% power to detect an absolute difference between the two arms of 12%, equivalent to a 37.5% increase in relative rate of follow-up with a PCP within 14 days of discharge. Given an estimated 20% attrition rate based on past studies in this population and setting, a total of 640 participants (320 per arm) were recruited for this study. Additional participants will be recruited and randomized to replace previously randomized participants who die during their hospitalization or who are never discharged from the hospital, since they will contribute no post-baseline data, including the primary outcome. The number of additional participants will be consistent with maintaining group balance using permuted blockrandomization (i.e., 1 or more blocks of size 6 or 8, depending on number of participants required).

4.2 Interim Analyses

No interim analyses will be performed

4.3 Statistical analyses

All analyses will follow the intention-to-treat principle.

The detailed statistical analysis plan for using ICES administrative data will be developed on a separate document per institutional requirements, but the analyses are summarized in this document as well.

4.3.1 Descriptive Statistics

Baseline participant characteristics by study arm will be summarized with counts and proportions for binary and categorical variables, and means and standard deviations, and medians and interquartile ranges, where appropriate. No statistical testing of baseline differences between the study arms will be performed, as recommended in the CONSORT statement and other publications [Moher, Senn, Pocock].

Descriptive statistics will also characterize the distribution of outcomes according to baseline characteristics by intervention arm.

We will also construct graphs to explore relationships and estimate correlations and associations between participant baseline characteristics and outcomes, overall and by subgroups.

To evaluate the magnitude of missing data from the baseline and 30-day interviews, the proportion of missing data for all outcomes and baseline variables by intervention arm will be also calculated.

4.3.2 Primary Outcome Analyses

The primary analysis of the primary outcome will be performed using the $\chi 2$ test to compare two independent proportions of 14-day PCP follow-up. The difference in proportions (risk difference) with 95% confidence interval (CI) will be estimated using the Wald method.

Secondary analyses of the primary outcome include estimating unadjusted effects of the intervention. The unadjusted risk ratio with 95% confidence interval (CI) will be estimated using the modified Poisson regression model including only the intervention arm indicator. The unadjusted odds ratio with 95% CI will be estimated from the logistic regression model including only the intervention arm indicator.

4.3.3 Secondary and Exploratory Outcomes Analyses

For secondary and exploratory outcomes, Table 1 and Table 2 display the statistical model and intervention effects according to outcome type (binary, continuous, time to event).

For binary outcomes, logistic regression models will be used to estimate odds ratios with 95% CIs. For count outcomes, Poisson or negative binomial regression models (if overdispersion is suggested by the data) will be used to estimate rate ratios with 95% CIs.

For continuous outcomes, linear (or another more outcome-specific distribution) regression models will be built.

For change in continuous outcomes from baseline to 30-days post-discharge, we will consider analysis of covariance (ANCOVA), adjusting for the baseline outcome value.

For time in days to re-admission or all-cause mortality after discharge, a survival analysis will be performed. Cumulative event rates will be calculated with the Kaplan-Meier method, with event or censoring times calculated from the date of discharge. Differences in Kaplan-Meier survival curves between the study arms will be assessed using the log-rank test. The Cox proportional hazards model will estimate the hazard ratio with 95% CI.

Multiple testing correction for p-values will be applied in the analyses of secondary outcomes using the Holm method.

For exploratory outcomes, in addition to 95 % CIs, we will also report p-values, since we agree with Pocock et al. (2021) that such p-values, although mostly characterized as being a form of descriptive statistics, can "help the reader focus on potentially important exploratory findings."

Table 1. Secondary Outcomes, Statistical Models and Measures of Intervention Effect by Outcome Type

Secondary Outcome	Outcome Type	Model	Intervention Effect (Unadjusted)
Number of ED visits within 30 days post-discharge	Count ≥0	Poisson or negative binomial regression including intervention arm indicator	Rate ratio with 95% CI, and p-value*
Number of ED visits within 90 days post-discharge	Count ≥0	Poisson or negative binomial regression including intervention arm indicator	Rate ratio with 95% CI, and p-value*
Composite of re-admission or all-cause mortality within 30 days post-discharge	Binary, 0/1	Logistic regression including intervention arm indicator	Odds ratio with 95% CI, and p-value*
Composite of re-admission or all-cause mortality within 90 days post-discharge	Binary, 0/1	Logistic regression including intervention arm indicator	Odds ratio with 95% CI, and p-value*

CI: confidence interval; ED: emergency department

^{*}Multiple testing correction for p-values will be applied using the Holm method.

Table 2. Exploratory Outcomes, Statistical Models and Measures of Intervention Effect by Outcome Type

Exploratory Outcome	Outcome Type	Model	Intervention Effect (Unadjusted)
Leaving against medical advice at discharge	Binary, 0/1	Logistic regression	Odds ratio with 95% CI, and p-value
Self-reported quality of care transition after hospital discharge (CTM-3) at the time of the 30-day interview	Continuous, range 0-100, unknown distribution	Linear regression or appropriate model for specific distribution type	Mean difference with 95% CI, and p-value
Self-reported change in difficulties meeting subsistence needs total score (Competing Priorities) at the 30-day interview post discharge relative to baseline, total score	Continuous, range 0-15	ANCOVA on change in total scores, with baseline value as covariate	Mean difference with 95% CI, and p-value
For participants who did not previously report contact with a case manager in the 30 days prior to the baseline interview, connection to a case manager in the community at the time of the 30-day interview	Binary, 0/1	Logistic regression	Odds ratio with 95% CI, and p-value
Medication adherence (MMAS-8) at the time of the 30-day interview	Continuous, range 0-8	Linear regression or appropriate model for specific distribution type	Mean difference with 95% CI, and p-value
Change in health status EQ-5D-3L at the time of the 30-day interview relative to baseline	Continuous, range -0.340 to 1.0 at each time point	ANCOVA on change in total scores, with baseline value as covariate	Mean difference with 95% CI, and p-value
Change in quality of life EQ-5D VAS at the time of the 30-day interview relative to baseline	Continuous, potential range 0-100	ANCOVA on change in total scores, with baseline value as covariate	Mean difference with 95% CI, and p-value
Days spent in hospital post-discharge within 90 days post-discharge	Count ≥0	Poisson or negative binomial regression including intervention arm indicator	Rate ratio with 95% confidence interval, and p-value

Days spent in hospital post-discharge within 180 days post-discharge	Count ≥0	Poisson or negative binomial regression including intervention arm indicator	Rate ratio with 95% confidence interval, and p-value
Time in days to re-admission or all-cause mortality after discharge, within 180 days post-discharge.	Time to event	Kaplan Meier curves with log-rank test Cox proportional hazards model	Hazard ratio with 95% CI, and p-value
Attendance of any non-PCP healthcare appointment within 180 days post-discharge	Binary, 0/1	Logistic regression	Odds ratio with 95% CI, and p-value

PCP: primary care physician; VAS: visual analog scale; ANCOVA: analysis of covariance; CI: confidence interval

4.3.4 Subgroup Analyses: For whom does the intervention work best?

To evaluate which patient subgroups may most benefit from the intervention with respect to the primary outcome, multivariable logistic regression models will estimate odds ratios with 95% confidence intervals to explore potential subgroup effects. Models will include each of the following pre-specified baseline covariates, in addition to the intervention arm indicator, one-at-a-time, and the corresponding interaction term with the intervention arm: age, sex, racial or ethnic identity, time of enrollment relative to study initiation (first or second half), self-reported current illicit drug use, self-reported current high-risk alcohol use, Charlson Comorbidity Index score (from ICES), and prior acute care utilization for a mental health reason (from ICES).

4.3.5 Sensitivity Analyses

For the primary outcome, we will evaluate whether a sensitivity analysis needs to be performed excluding the 16 patients who were asked the 3 original questions about visiting a PCP within 14 days. Determination will depend on whether, for these cases, the only indicator of the visit was by self-report.

For the Competing Priorities exploratory outcome, we will also compare groups using 3 alternative scoring methods. The first method calculates, for each participant, the mean score across all 5 items, range 1-4 (each item is scored on a 1–4 scale, with Never = 1; Rarely = 2; Sometimes = 3; and Usually = 4). The second method dichotomizes the mean score to participants with frequent (>3) versus infrequent (≤3) competing priorities. The third method classifies participants as having competing priorities if they responded "Usually" to any of the 5 items. For the first method, we will fit an analysis of variance (ANOVA) model. For the binary outcomes, we will fit generalized estimating equations, for the binomial distribution with logit link. Models will include the intervention arm indicator, time (30-day versus baseline interview), and the interaction of intervention arm by time. A significant interaction will indicate that the change from baseline is different between the study groups.

The total MMAS-8 score can also be categorized into three levels of adherence: high adherence (score = 8), medium adherence (score of 6 to < 8), and low adherence (score< 6). We will compare the groups using the Cochran-Armitage test for trend.

For binary outcomes outlined in Tables 1 and 2, and subgroup analyses, we will also fit modified Poisson regression models to estimate risk ratios with 95% CIs. All analyses will be conducted using R, STATA, and SAS. All statistical tests will be two-sided and a p-value of 0.05 or less will indicate statistical significance.

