Appendix 2 Self-Reported Measures and Scoring Algorithms

Details of the instruments used to evaluate exploratory self-reported outcomes are described below:

1 CTM-3: Three-Item Care Transitions Measure

The CTM-3 is a measure designed to evaluate the extent to which patients believe the healthcare team accomplished essential care processes in preparing them for discharge and participating in post-hospital self-care activities. This measure was endorsed by The National Quality Forum (www.qualityforum.org).

Each of the three items is scored on a 1–4 scale, with Strongly Disagree=1; Disagree=2; Agree=3; and Strongly Agree=4. For each participant, the mean score is calculated by summing up the responses across the 3 items and dividing by the number of items answered (https://mhdo.maine.gov/pdf/NQF_CTM_3_%20Specs_FINAL.pdf).

The mean score (mean_ctm3) is then re-scaled to a 0-100 score (CTM3_score) using the following formula:

```
CTM3_score=(new_max - new_min) / (old_max - old_min) * (mean_ctm3 - old_min) + new_min,
```

where new max=100; new min=0; old max=4; old min=1.

Higher scores indicate better care transition experiences. This continuous variable has been used in a variety of studies.

2 Competing Priorities

This measure is a validated 5-item measure of frequency of difficulty in meeting the following needs over the past 30 days: shelter, food, clothing, a place to wash, and access to a bathroom (Koegel et al, 1996; Gelbert et al, 1997).

Each item is scored on a 1–4 scale, with Never=1; Rarely=2; Sometimes=3; and Usually=4. There is no consensus on how to best score this instrument. We are aware of four scoring methods.

The first method calculates, for each participant, the mean score across all 5 items (Koegel et al, 1996, range 1-4).

The second method dichotomized the mean score to participants with frequent (>3) versus infrequent (≤ 3) competing priorities (Gelbert et al, 1997).

The third method classifies participants as having competing priorities if they responded "Usually" to any of the 5 items (Hwang et al, 2010).

The fourth method, re-scales items to a range of 0 to 3, and calculates the total score as their sum (Baggett et al, 2018, range 0-15).

3 MMAS-8: Eight-Item Morisky Medication Adherence Scale (purchased license to use)

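### Does listing the Competing Priorities item mean as an alternative scoring, when it is a rescaling of the main total, call for a change to the SAP?

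*SAP*

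**What the plan says.** Appendix 2 of the SAP says of this scale that "There is no consensus on how to best score this instrument" and lists four published methods. The one used for the main analysis is the last: "The fourth method, re-scales items to a range of 0 to 3, and calculates the total score as their sum", giving a range of 0 to 15. Table 2 in section 4.3.3 analyses that total by ANCOVA on change, with the baseline score as covariate.

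Section 4.3.5 adds the other three methods as sensitivity analyses: "For the Competing Priorities exploratory outcome, we will also compare groups using 3 alternative scoring methods". On the mean score it says: "The first method calculates, for each participant, the mean score across all 5 items, range 1-4". Method 2 cuts that mean at 3, and method 3 asks whether any item was answered at the most frequent level. On the models it says: "For the first method, we will fit an analysis of variance (ANOVA) model"; the two binary codings get generalized estimating equations (GEE). Then: "Models will include the intervention arm indicator, time (30-day versus baseline interview), and the interaction of intervention arm by time". The result is to be read as follows: "A significant interaction will indicate that the change from baseline is different between the study groups".

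For the CTM-3, Appendix 2 handles unanswered items by "dividing by the number of items answered". It gives no such rule for Competing Priorities.

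**The concern.** A sensitivity analysis should vary the feature whose influence is in question. Here that feature appears to be the scoring, yet a mean and a sum of the same five items differ only in units. A reader who sees method 1 agree with the main result might conclude that the finding is robust to scoring, and one who sees it disagree might conclude that scoring matters. With complete items neither conclusion would be justified, because only the model, and possibly the set of participants, has changed.

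Two smaller points add to the unease. The ANOVA sentence does not say that the two measurements on each participant are treated as correlated. And without a rule for unanswered items, the mean and the total could diverge for reasons unrelated to scoring. At stake is the interpretation of one supporting analysis of an exploratory outcome.

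**Working it through.** **Inputs.** From the SAP: items coded 1 to 4, method 1 as their mean, and the main score as the sum of items recoded 0 to 3 (section 4.3.5, Appendix 2); ANCOVA on change for the total (Table 2); arm, time and arm-by-time for method 1 (section 4.3.5); 256 per arm after 20% attrition from 320 (section 4.1, stated for the primary outcome). Assumed, because the SAP gives no figures: baseline-to-30-day correlation r = 0.3, 0.5 or 0.7, equal variances at the two times, and the section 4.1 attrition applying to this scale.

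**1. The stated ranges and the identity.** With items x1 to x5, total = sum of (xi - 1) = 5 x mean - 5 = 5 x (mean - 1). A mean of 1 gives 0 and a mean of 4 gives 15, which reproduces both ranges in the SAP. Enumerating all 4^5 = 1,024 complete answer patterns shows no departure from the identity.

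**2. Same model, same test.** In one simulated data set with 256 per arm, the ANCOVA arm effect was -0.948 on the total and -0.190 on the mean, a ratio of 5, with t = -4.089 and p = 0.00005 for both.

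**3. Methods 2 and 3.** A mean above 3 is the same as a total of 11 or more, so method 2 is a cut of the same score; it discards information but is a different analysis. Method 3 is not a function of the total: for totals from 3 to 10 a participant can fall either way. Both remain different codings of the answers.

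**4. What the change of model costs.** For complete pairs, the repeated-measures interaction has variance proportional to 2(1 - r) and the ANCOVA to 1 - r^2, so the SE ratio is sqrt(2/(1 + r)). Keeping baseline-only participants in a mixed model gives, per arm, (1 - r^2)/256 + (1 - r)^2/320 against (1 - r^2)/256.

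| r | SE ratio, complete pairs | Power where ANCOVA has 80% | SE ratio, baseline-only kept | Power |
|---|---|---|---|---|
| 0.3 | 1.24 | 62% | 1.20 | 65% |
| 0.5 | 1.15 | 68% | 1.13 | 70% |
| 0.7 | 1.08 | 73% | 1.07 | 75% |

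The arm-by-time test is thus somewhat less precise, but valid.

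**5. How far the two p-values can part.** By normal approximation for complete pairs, with no true effect the median absolute gap is 0.18, 0.15 and 0.12 for the three correlations. At the effect giving the ANCOVA 80% power it is 0.017, 0.010 and 0.005, and the two analyses fall on different sides of 0.05 in about 23%, 17% and 11% of trials. All of this comes from the model and none from the scoring.

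**6. Independent errors.** If the ANOVA were fitted with only the named terms and no allowance for pairing, the SE would be too large by 1/sqrt(1 - r) = 1.20, 1.41 and 1.83, so the test would err towards caution.

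**7. Unanswered items.** If one item is missing and the mean m is taken over the four answered, the rescaled mean is 5(m - 1) and the plain sum of answered items is 4(m - 1). The difference is m - 1, between 0 and 3 points, and is zero in only 5 of the 5 x 256 = 1,280 patterns. That would be an effect of the missing-item rule.

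**The case for a change.** The case for acting is that the identity is exact, the label says scoring, and one or two sentences would prevent a misreading at no data cost. The algebra stands in full, and so does the consequence that agreement between method 1 and the total says nothing about scoring.

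The case weakens at the possible remedies:

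- **Fitting method 1 with the same ANCOVA** would reproduce the main p-value and add only a change of units.
- **Dropping it** would remove the only continuous analysis that shares the arm, time and arm-by-time structure of methods 2 and 3, and with it a useful reference for them.
- **Relabelling it** as a model check is accurate but alters no estimate or test.
- **Stating the clustering** fills in what a competent analyst would do anyway: the companion models are GEE, and the interaction is read as a difference in change from baseline.
- **Stating a missing-item rule** is similar. The definition of the mean refers to all five items, and section 4.4.3 plans multiple imputation, with details to follow.

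The label itself also carries little weight. The same section holds the three-level MMAS-8 categories and the modified Poisson risk ratios, so it works as a list of additional analyses. Reporting each published metric when none is agreed is a sensible aim.

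**Conclusion.** The observation is true, but the plan needs no change. With complete items, method 1 is the main score in other units, and its comparison with the main result is a comparison of models and of the participants each keeps. The SAP draws no conclusion about robustness from it, the planned test is valid on the natural repeated-measures reading, and methods 2 and 3 still vary the coding. The loss of precision relative to the ANCOVA is 8% to 24% in standard error for complete pairs, resting on assumed correlations of 0.7 down to 0.3 and equal variances. It falls on a supporting analysis of one exploratory outcome, for which the SAP makes no power claim. The main ANCOVA of this scale and the primary and secondary outcomes are unaffected. When the results are read, agreement between method 1 and the total should be taken as agreement between models.

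### The Competing Priorities mean-score ANOVA in 4.3.5 names no participant effect, so if fitted as written its arm-by-time test ignores the pairing and is conservative

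*SAP*

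**What the plan says.** SAP 4.3.5 (Sensitivity Analyses) adds three alternative scorings of the Competing Priorities measure: the five-item mean (range 1 to 4), that mean dichotomized at 3, and an indicator of answering in the top category on any item.

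- For the mean: "For the first method, we will fit an analysis of variance (ANOVA) model".
- For the two dichotomies: "For the binary outcomes, we will fit generalized estimating equations, for the binomial distribution with logit link".
- For all of them, one shared list of terms: "Models will include the intervention arm indicator, time (30-day versus baseline interview), and the interaction of intervention arm by time".
- The reading rule: "A significant interaction will indicate that the change from baseline is different between the study groups".
- The significance level: "All statistical tests will be two-sided and a p-value of 0.05 or less will indicate statistical significance".

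The main analysis of the same measure is in Table 2 (section 4.3.3). It uses the 0 to 15 total and is specified as "ANCOVA on change in total scores, with baseline value as covariate". Appendix 2 defines that total as the sum of the same five items, each rescaled to 0 to 3.

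Neither 4.3.5 nor any other section of the SAP gives a participant term, a within-person covariance or a clustered standard error for the mean-score ANOVA.

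**The concern.** Because time is a factor in the model, each participant who completes both interviews supplies two records. GEE is a method for correlated records, so the two binary scorings have a means of handling the pairing. The mean score, built from the same answers by the same people, is given a model whose listed terms do nothing to link a person's two values.

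An analyst who fits exactly those terms uses the between-person residual variance to test a within-person contrast. If a person's two scores are positively correlated, the interaction standard error is too large, the confidence interval too wide and the p-value too high. The plan judges this check by whether the interaction is significant. A real difference in change could therefore appear to fail a scoring sensitivity analysis because of the error term and not because of the scoring.

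**Working it through.** **The plan's own figure.** The SAP states no figure for this ANOVA. Its one reproducible design figure is the primary-outcome sample size in 4.1 (32% versus 44%, two-sided 0.05, 80% power):

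n = [1.96 × sqrt(2 × 0.38 × 0.62) + 0.8416 × sqrt(0.32 × 0.68 + 0.44 × 0.56)]² / 0.12² = 255.7, so 256 per arm. The power at 256 is 0.8005, and 256/0.80 = 320 per arm.

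This agrees with the SAP. Below, 256 and 320 serve only as realistic sizes.

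**Inputs.** Terms are arm, time and arm-by-time (4.3.5); alpha is 0.05 two-sided (4.3.5); allocation is 1:1 (1.1); attrition is 20% (4.1). Assumed, because the SAP does not give them: within-person correlation rho of 0.3, 0.5 or 0.7; equal variance s² at both interviews; and s = 0.8 for the simulation. The standard-error ratio does not depend on s.

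**Complete pairs, n per arm.** The interaction estimate is a contrast of four cell means.

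- Variance if all records are independent: 4s²/n.
- Actual variance: 2 × [2s²(1 - rho)/n] = 4s²(1 - rho)/n.
- Model SE / true SE = 1/sqrt(1 - rho).
- Actual type I error = 2 × [1 - Phi(1.96/sqrt(1 - rho))].
- Power where a correct within-person test has 80% = Phi(2.80 - 1.96/sqrt(1 - rho)).

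| rho | SE ratio | Actual type I error | Power (correct test 80%) |
|---|---|---|---|
| 0 | 1.00 | 5.0% | 80% |
| 0.3 | 1.20 | 1.9% | 68% |
| 0.5 | 1.41 | 0.6% | 51% |
| 0.7 | 1.83 | 0.03% | 22% |

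**Missing 30-day interviews.** Take 320 per arm at baseline and 256 at 30 days, missing at random with respect to the scores. Per arm the model uses s²(1/256 + 1/320), and the actual variance is s²(1/256 + 1/320 - 2 × rho/320). At rho 0.5 the ratio is sqrt(0.00703/0.00391) = sqrt(1.8) = 1.34.

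**Simulation at rho 0.5 (4,000 trials per setting).** With 256 complete pairs per arm, the mean model SE was 0.100, the empirical SE 0.070 and the type I error 0.5%. With 320 per arm and 20% missing at 30 days, these were 0.095, 0.071 and 0.8%. Across all settings (rho 0 to 0.7, with and without missing interviews), a change-score test held its level, with type I error between 4.6% and 5.5%.

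**Relation to the main score.** With all five items answered, total = 5 × mean - 5, so mean = 1 + total/5. The two scorings are exact linear rescalings of each other. ANCOVA gives the same arm effect whether the dependent variable is the change or the 30-day value, so ANCOVA on the mean would return the Table 2 t-statistic and p-value, with the estimate divided by 5.

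**The case against.** The strongest reply is that this is an omission and not a stated error. The SAP nowhere says that the two scores are independent. The list of terms is shared with the GEE models, for which no cluster variable or working correlation is named either, so it may be only the list of fixed effects. An ANOVA with a baseline/30-day factor, read as a test of differential change, fits a repeated-measures ANOVA. That reading is plausible, and it is why the point is limited to the model as written. It does not remove the point: the text does not supply the structure, and following it literally gives the wrong error term.

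Three stronger inferences are tempting and are not supported.

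- *That the trial's findings are at risk, or that false positives rise.* With positive correlation the error runs the other way. Table 2 uses one record per person and is untouched, as are the primary and secondary analyses.
- *That a real effect would fail this check.* It might. The loss depends on rho, which the SAP does not give, and at rho 0.3 it is moderate.
- *That ignoring the pairing makes the ANOVA standard error 1.63 times that of the main ANCOVA at rho 0.5.* The ratio sqrt(2/(1 - rho²)) is indeed 1.63, but sqrt(2/(1 + rho)) = 1.15 of it is the ordinary efficiency gap between change-score analysis and ANCOVA. Only the factor 1.41 comes from the pairing (1.15 × 1.41 = 1.63, from unrounded values).

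It is also fair to say that 4.3.3 treats exploratory p-values as largely descriptive, and that this is one of three alternative scorings of one exploratory outcome.

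**Conclusion.** The point holds for the model as specified; its priority is minor. Fitted with only the listed terms, the mean-score ANOVA overstates the interaction standard error by 1/sqrt(1 - rho) with complete pairs: about 1.20, 1.41 and 1.83 at rho 0.3, 0.5 and 0.7. With missing 30-day interviews the factor is somewhat smaller, about 1.34 at rho 0.5 with 20% missing. The consequence is a conservative check that could make a real effect look fragile.

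This rests on an assumed rho, equal variances at the two interviews and, for the 1.34, missingness unrelated to the scores. It also needs rho to be positive, which is to be expected of the same scale answered twice by the same person. A negative rho would reverse the direction (SE ratio 0.91 and type I error 7.4% at rho -0.2).

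**What to change.** Replace the ANOVA sentence in 4.3.5 with one that names the within-person structure. For example: for the mean score, a linear mixed model with arm, time and arm-by-time as fixed effects and participant as a random effect. A repeated-measures ANOVA, or a GEE with identity link and participant as the cluster, would serve as well and would match the GEE already planned for the binary scorings. The mixed model and GEE can also keep the baseline records of people without a 30-day interview.

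ANCOVA on the mean score is not a useful replacement. Because of the linear rescaling, it would only repeat the Table 2 result when all items are answered.

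The cost is one sentence in the SAP. No new data are needed and no other analysis changes.
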